#### **6.6.5 Comparison of Parent/Caregiver and Patient Perceptions of AV Severity and Impact**

Parent/caregiver and pediatric patient responses to the questions related to AV severity at Baseline and Week 12 will be compared and reported using descriptive statistics, to portray the

level of concordance/discordance in stakeholder perceptions, within the Subject age group of 12-17 yrs. This analysis will be conducted using FAS.

Responses to select EPQ items at Baseline and Week 12 related to worries about Acne and impact of acne on child's ability to reach future goals will be compared to corresponding questions to parents/caregivers to portray the level of concordance/discordance in stakeholder perceptions, within the Subject age group of 12-17 yrs. This analysis will be conducted using FAS.

Parent/caregiver and pediatric patient responses to the questions at Week 12 related to the parents' understanding of child's concerns will be compared and reported using descriptive statistics, to portray the level of concordance/discordance in stakeholder perceptions, within the Subject age group of 12-17 yrs. This analysis will be conducted for the entire relevant cohort using FAS.

No missing data imputation will be undertaken for these items.

## 6.7 Prior and Concomitant Medications

Medication usage is coded using the latest (2022) WHO Drug Dictionary. Medications are presented by WHO Drug Anatomical/Therapeutic/Chemical (ATC) category and WHO Drug preferred name. Summaries are presented for prior (prior to the first dose of study treatment, gathered as aggregate indicators as well as at individual item level) medication use and concomitant (after first dose of study treatment had been given, gathered at individual item level) medication use. Medications with an end date occurring before the first study treatment (sarecycline) dose date in the treatment period are identified as prior medications. Medications with a start date occurring on or after the first study treatment (sarecycline) dose date in the treatment period or medications with a start date prior to the first (sarecycline) dose that were ongoing or with end dates that were on or after the first treatment (sarecycline) start date are identified as concomitant medications.

Concomitant Acne and non-Acne medications are captured at Baseline and at the study end (Week-12) to characterize the use of concomitant medications among the study cohort. Accordingly, the Acne and non-Acne concomitant medication use will respectively be summarized in aggregate for the 3-month study observation period, and not separated by study visits.

Contraceptive medications (part of non-Acne concomitant medications) will be grouped into single class/group of medications, irrespective of the route of administration or active ingredients, as reported from patient medical charts.

All summaries present the number (%) of subjects for each medication. The denominators for calculating the percentages are based on the number of subjects in the FAS population.

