### **6.4.1 Reasons for Withdrawal**

Subjects are free to withdraw from participation in the study at any time upon request.

A Site Investigator may terminate a study subject's participation in the study if:

- Any medical condition, event or situation occurs such that continued participation in the study would not be in the best interest of the subject. This may include pregnancy among female subjects.
- In the event Subjects are unable to swallow the sarecycline tablets after enrollment, they will be discontinued from the study and the reason for study discontinuation will be recorded as the inability to swallow tablet.
- The subject meets a study exclusion criterion (either newly developed or not previously recognized) that precludes further study participation.

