Each AE, either serious or non-serious for which a causal relationship to sarecycline cannot be excluded, was considered as an ADR. An ADR is an injury caused by taking medication. ADRs may occur following a single dose or prolonged administration of a medicinal product or result from the combination of two or more medicinal products.

The determination of whether an AE is related to study treatment (sarecycline) was based on information regarding the degree to which the study treatment had caused or contributed to the event and will be categorized per the following criteria:

- Related: There were good reasons and sufficient information (e.g. plausible time sequence, dose-response relationship, pharmacology, positive de-challenge and/or re-

challenge) to assume a causal relationship with the study medication in the sense that it is plausible, conceivable or likely.

- **Not Related:** There were good reasons and sufficient information (e.g. implausible time sequence and/or attributable to concurrent disease or other drugs) to rule out a causal relationship with the study medication.

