### 6.2 Analysis Populations and Datasets

Statistical analysis and data tabulation will be performed using the following analysis populations unless specified otherwise:

- **Safety Population:** All patients who received at least one dose of sarecycline during the study observation period, as part of usual care. This in essence constitute all 300 Subjects recruited into the study.
- **Full Analysis Set (FAS):** All patients within the Safety Population that had at least one question answered pertaining to study primary research objective. This in essence will constitute all Subjects who completed their Week-12 survey. By definition, this would exclude all Subjects who were terminated (for any reason) at any timepoint (prior to Week-12) in the study.

In the event that the safety population and FAS differ, all safety evaluations (part of additional objectives) will be conducted among the safety population, while FAS will be used to conduct

analyses addressing rest of the study objectives, including the description of population demographics, primary and secondary objectives, and select additional (non-safety related) objectives.

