## **6.8 Safety Assessments**

The safety data will be analyzed descriptively using Safety Population dataset, to report the frequency of occurrences of AEs/ADRs and SAEs. MedDRA database version 2021AB will be used for coding the AEs and ADRs. These will be reported at individual item level as well in aggregate at specific category level (e.g., GI effects, vestibular effects) for each of the subject encounter timepoints (4, 8 & 12 weeks post-index date). The number of patients discontinuing treatment for any reason and the number of patients discontinuing the study because of AEs/ADRs will be assessed within the entire study observation window (of 12 weeks), as documented in patient medical charts and reported in study EDC portal.

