## 7.2 Tables from clinician's DCF (FAS Population)

Clinician data is analyzed using the FAS dataset. In relevant instances (such as IGA and physician satisfaction evaluations), only FAS dataset with corresponding week 12 clinician data is used. All data tables in this section correspond to FAS population.

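### Prescribed-dose and prior/concomitant-medication tables cover only Week-12 completers, while adverse events cover all 300 treated subjects

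*SAP*

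**What the plan says.** **Medication and dose.** SAP section 6.7 states: "The denominators for calculating the percentages are based on the number of subjects in the FAS population". SAP section 7.2 holds Table 7.2.5 (dose and frequency by visit), 7.2.6.1 (prior acne treatment), 7.2.6.2 (acne concomitant medication) and 7.2.7 (other concomitant medication), and says: "All data tables in this section correspond to FAS population".

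**Who is in the FAS.** SAP section 6.2 says of the FAS: "This in essence will constitute all Subjects who completed their Week-12 survey". It continues: "By definition, this would exclude all Subjects who were terminated (for any reason) at any timepoint (prior to Week-12) in the study". The introduction to SAP section 7 repeats the completer reading.

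**Safety.** SAP section 6.8 says: "The safety data will be analyzed descriptively using Safety Population dataset, to report the frequency of occurrences of AEs/ADRs and SAEs". Of the Safety Population, SAP section 6.2 says: "This in essence constitute all 300 Subjects recruited into the study".

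**Collection.** Appendix A of both documents marks sarecycline dose at every encounter. It marks both concomitant-medication rows at Baseline and Week 12. It also marks all three rows at the Early Termination visit. SAP section 6.7 names only Baseline and Week 12 as capture times for concomitant drugs.

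**Termination.** Protocol section 6.2 excludes patients currently on penicillin or oral retinoids. Protocol section 6.4.1 lists, among the grounds on which an investigator may end participation: "The subject meets a study exclusion criterion (either newly developed or not previously recognized) that precludes further study participation".

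**The concern.** An adverse event in a subject terminated at Week 6 is counted. The tables that describe what that subject was prescribed, and what else the subject was taking, leave the subject out. The SAP's own ADR definition (section 5.6.1) says that a reaction may "result from the combination of two or more medicinal products", so co-medication is part of what a reader needs when interpreting the ADR tables.

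The omission need not be neutral. Starting an excluded drug is one possible route to termination. A subject who starts isotretinoin and is terminated for it cannot appear in Table 7.2.6.2, although that table has an isotretinoin row. At stake is the description of dose and co-medication behind the safety and tolerability objective, not the effectiveness results.

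**Working it through.** The plan gives no figure to reproduce on this point. The check is a comparison of populations, followed by an illustration of size.

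**1. Which planned output shows what for a subject terminated before Week 12**

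| Information | Where planned | Early-terminated subject shown? |
|---|---|---|
| AEs, ADRs, SAEs | Tables 7.4.4.1 to 7.4.4.12, Safety Population | Yes |
| Dose action taken because of an AE or ADR | Same tables; per event in listings 7.4.4.9 and 7.4.4.12 | Yes, though the overall summaries merge everything except withdrawal into Other Actions |
| Study and treatment duration | Table 7.4.2, Safety Population | Yes |
| Compliance | Section 6.6.2 and Table 7.4.3, Safety Population | Yes |
| Discontinuation, disposition | Section 6.8 and Table 7.4.7 | Yes |
| Prescribed dose and frequency by visit | Table 7.2.5, FAS | No |
| Dose changes not linked to an AE | Only through Table 7.2.5, FAS | No |
| Prior acne treatment | Table 7.2.6.1, FAS | No |
| Concomitant medication | Tables 7.2.6.2 and 7.2.7, FAS | No |

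Listings 7.4.4.9 and 7.4.4.12 give onset, resolution, action, intensity and seriousness. They have no field for dose level or co-medication. Table 7.4.8 will summarise significant deviations, but the SAP does not say that it will name a drug.

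**2. How many subjects are affected**

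SAP section 6.1 expects attrition but gives no rate. Let d be the assumed proportion terminated early. Then the number omitted is E = 300 × d, and the FAS is F = 300 − E.

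- d = 5%: E = 15, F = 285
- d = 10%: E = 30, F = 270
- d = 15%: E = 45, F = 255
- d = 20%: E = 60, F = 240

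**3. How far a percentage could move**

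Assume, for illustration only, that a drug is used by 20% of completers and 40% of early-terminated subjects. The FAS table shows 20.0% whatever d is. The Safety Population value is (0.20 × F + 0.40 × E) / 300:

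- d = 5%: (57 + 6) / 300 = 21.0%
- d = 10%: (54 + 12) / 300 = 22.0%
- d = 15%: (51 + 18) / 300 = 23.0%
- d = 20%: (48 + 24) / 300 = 24.0%

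The extreme case is an excluded drug whose every new user is terminated. If 3, 6 or 9 subjects start it, the FAS table shows 0%, against 3/300 = 1.0%, 6/300 = 2.0% or 9/300 = 3.0%. The usage rates and counts are assumptions; the documents support none of them in particular.

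**The case against.** The strongest reply is that Section 7.4 already covers most of what a safety reader needs. That stands for several items, and it rules out stronger readings that a reader might infer:

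- **That dose changes in early stoppers are never reported.** Not supported. The recorded actions include dose reduced and dose increased, and both patient-level listings show the action for each event. What is missing is the prescribed dose itself and any change not tied to an AE.
- **That exposure exists only for completers, or that stopping is understated.** Not supported. Duration, compliance, discontinuation and disposition are all planned on the Safety Population. Table 7.2.5 has no row for stopping, so it could not understate it.
- **That every subject who stops sarecycline is lost.** Not supported. The FAS leaves out those terminated from the study. Someone who stops the drug but answers the Week-12 survey meets the FAS definition.
- **That every user of an excluded drug vanishes.** Not supported. Termination is at the investigator's discretion, so some may remain in the FAS.

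Two further objections stand in part. First, collection is not assured. Protocol section 7.6 makes early-termination assessments conditional on feasibility and refers to those due at the next encounter, and Appendix A schedules no concomitant-medication record at Weeks 4 or 8. For some early stoppers only the baseline drug list may exist. That limits how complete the repaired tables can be, but it does not justify dropping the baseline records as well. Second, aggregate percentages do not tie a drug to a particular reaction. Safety Population tables would show the dose and co-medication of the group in which the events are counted, and no more than that.

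**Conclusion.** The point holds in a limited form. The SAP counts adverse events in all treated subjects but describes prescribed dose and prior and concomitant drugs only in Week-12 completers. For those terminated early, nothing planned shows prescribed dose, dose changes not linked to an AE, or co-medication.

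The number affected cannot be derived from the documents. With assumed early termination of 5% to 20%, it is 15 to 60 of 300, taking the SAP at its word that all 300 recruited subjects received a dose. Under the 20%/40% usage illustration, a drug percentage would move by 1 to 4 percentage points over that range. No primary or secondary endpoint and no AE count is affected. The change is still worth making because the omission is selective, it bears on a stated safety objective, and it is cheap to repair.

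**What to change.** - In SAP section 6.7 and Section 7.4, also produce Tables 7.2.5, 7.2.6.1, 7.2.6.2 and 7.2.7 on the Safety Population, with a separate column for early-terminated subjects. Keep the FAS versions beside the effectiveness tables.
- Use the baseline records for all subjects, the Week 4 and Week 8 records for dose, and the Early Termination record where it exists.
- Add the Early Termination visit to the capture times in section 6.7, to match Appendix A.
- In the overall AE and ADR summaries, split Other Actions into the action categories listed in SAP section 5.6.1.
- Footnote how many early-terminated subjects have no concomitant-medication record after baseline.

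The cost is a few extra runs of tables that are already specified. There are no new visits or data items. The SAP already does the same for demographics, which Tables 7.4.5 and 7.4.6 repeat on the Safety Population. The drawback is incomplete concomitant-medication data for some early stoppers, which the footnote makes visible.

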## **6.8 Safety Assessments**

The safety data will be analyzed descriptively using Safety Population dataset, to report the frequency of occurrences of AEs/ADRs and SAEs. MedDRA database version 2021AB will be used for coding the AEs and ADRs. These will be reported at individual item level as well in aggregate at specific category level (e.g., GI effects, vestibular effects) for each of the subject encounter timepoints (4, 8 & 12 weeks post-index date). The number of patients discontinuing treatment for any reason and the number of patients discontinuing the study because of AEs/ADRs will be assessed within the entire study observation window (of 12 weeks), as documented in patient medical charts and reported in study EDC portal.

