In two pivotal RCTs, after 12 weeks of treatment, statistically significantly more recipients of once-daily sarecycline 1.5 mg/kg (as tablets) than of placebo achieved treatment success on the face; for those affected, acne on the chest and back also improved statistically significantly with sarecycline (Moore et al, 2018; Deeks, 2019). Sarecycline was generally well tolerated; other broad-spectrum tetracycline-class antibiotics are often associated with certain gastrointestinal, vestibular and phototoxic adverse effects and, in females, vaginal yeast infections, although these treatment-emergent adverse events were generally uncommon with sarecycline. As importantly, sarecycline was associated with HRQoL benefits, depicted by more favorable outcomes measured using Skindex-16 questionnaire (Moore et al, 2018; Deeks, 2019).

The clinical trial results of sarecycline highlight the clinical and QoL benefits derived by the acne patients. The demonstration of sarecycline-related benefits, including its impact on patient HRQoL in real world community practice settings is warranted to highlight sarecycline value proposition to patients, clinicians and payers alike. The ASIS questionnaire, along with the complimentary novel Expert Panel Questionnaire on patient HRQoL could be beneficial to use for research in community practice settings.

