#### **12.6.6 Safety Assessments**

The safety data will be analyzed descriptively using Safety Population dataset (if it is different from FAS), to report the frequency of occurrences of AEs/ADRs and SAEs. These will be reported at individual item level as well in aggregate at specific category level (e.g., GI effects, vestibular effects) for each of the subject encounter timepoints (4, 8 & 12 weeks post-index date). The number of patients discontinuing treatment within the 3-month post-index date, and number of patients discontinuing the study within the entire study observation window (of 12 weeks) because of AEs/ADRs will be reported, as documented in patient medical charts.

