**Table 7.4.4.1. Overall Summary of Adverse Events – Any Type (Subject Level)**

N=300	
[P4 or P5] Subjects with at least 1 adverse event (any type)*	n (%)
[P4_i_4 or P5_i_4]: Intensity of adverse event, among Subjects with at least 1 adverse event (any type)*	
R1: Mild	n (%)
R2: Moderate	n (%)
R3: Severe	n (%)
[P4_i_3 or [P5_i_3]: Action taken with Seysara, among Subjects with at least 1 adverse event (any type)*	
[P4_i_3r1 or P5_i_3r1]: Drug withdrawal / study discontinuation	n (%)
Other Actions	n (%)
[P4_i_5 or [P5_i_5]: Subjects with at least 1 SAE or Serious ADR	n (%)
Subjects with at least 1 SAE or Serious ADR resulting in death	n (%)

\*includes not related AEs and ADRs (related-AEs); excludes special safety events.

Note: Percentages were based on the total number of subjects in the study.

Deaths, AEs/ADRs, SAEs, and Serious ADRs were those that started on or after the date of the first dose of the study treatment and no more than 30 days after the date of the last dose of the study treatment.

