**Table 7.4.4.3. AEs (Not-Related) – by Organ Class & Preferred Term (Subject level)**

System Organ Class: Preferred Term	N=300	Intensity	Action Taken*
			Action Taken*
Gastrointestinal disorders	n (%)		
GI Upset	n (%)	A	A
Y	n (%)	B	B
Infections and infestations	n (%)		
X	n (%)	A	A
Y	n (%)	B	B
Injury, poisoning and procedural complication	n (%)	A	
X	n (%)	B	A
Y	n (%)		B
Investigations	n (%)	A	
X	n (%)	B	A
Y	n (%)		B
Nervous system disorders	n (%)	A	
Headache	n (%)	B	A
Y	n (%)		B
Skin and subcutaneous tissue disorders	n (%)	A	
X	n (%)	B	A
Y	n (%)		B
Respiratory, thoracic and mediastinal disorders	n (%)		
X		A	
Y	n (%)	B	A
General disorders and administration site conditions	n (%)		
X	n (%)	B	A
Y	n (%)		B

\*Action taken as a result of the AE.

Note: Percentages were based on the total number of patients in Safety Population, i.e., 300.  
If a same AE occurred more than once for a given patient, the AE was counted only once at Subject-level.  
For any of the safety events, a single patient may have reported more than one event.  
Deaths, AEs and SAEs were those that started on or after the date of the first dose of the study treatment  
and no more than 30 days after the date of the last dose of the study treatment.  
Adverse events were coded using MedDRA version 2021AB.

*This table will be replicated to characterize SAEs, if any observed.*

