**Table 7.4.4.5. ADRs – by Organ Class & Preferred Term (Subject level)**

System Organ Class: Preferred Term	N=300	Intensity	Action Taken*
			Action Taken*
Gastrointestinal disorders	n (%)		
GI Upset	n (%)	A	A
Y	n (%)	B	B
Infections and infestations	n (%)		
X	n (%)	A	A
Y	n (%)	B	B
Injury, poisoning and procedural complication	n (%)		
X	n (%)	A	A
Y	n (%)	B	B
Investigations	n (%)		
X	n (%)	A	A
Y	n (%)	B	B
Nervous system disorders	n (%)		
Headache	n (%)	A	A
Y	n (%)	B	B
Skin and subcutaneous tissue disorders	n (%)		
X	n (%)	A	A
Y	n (%)	B	B
Respiratory, thoracic and mediastinal disorders	n (%)		
X	n (%)	A	A
Y	n (%)	B	B
General disorders and administration site conditions	n (%)		
X	n (%)	A	A
Y	n (%)	B	B

\*Action taken as a result of the AE.

Note: Percentages were based on the total number of patients in Safety Population, i.e., 300.  
If a same ADR occurred more than once for a given patient, the ADR was counted only once at Subject-level. For any of the safety events, a single patient may have reported more than one event.  
Deaths, ADRs and Serious ADRs were those that started on or after the date of the first dose of the study treatment and no more than 30 days after the date of the last dose of the study treatment.  
Adverse events were coded using MedDRA version 2021AB.

*This table will be replicated to characterize Serious ADRs, if any observed.*

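### The safety table shells do not deliver the category-by-encounter adverse event frequencies promised in SAP 6.8, and they divide female-only events by both sexes

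*SAP*

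**What the plan says.** SAP 6.8 describes the safety analysis as frequencies of AEs, ADRs and SAEs in the Safety Population, shown item by item "as well in aggregate at specific category level (e.g., GI effects, vestibular effects) for each of the subject encounter timepoints". Protocol 12.6.6 makes the same commitment: "for each of the subject encounter timepoints (4, 8 & 12 weeks post-index date".

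The shells that should carry this out are Tables 7.4.4.1 to 7.4.4.14:

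- **Subject-level tables (7.4.4.1 to 7.4.4.5).** Each has a single count column headed N=300. The note to Table 7.4.4.1 reads "Percentages were based on the total number of subjects in the study"; the note to Table 7.4.4.5 reads "Percentages were based on the total number of patients in Safety Population, i.e., 300".
- **Organ-class and preferred-term tables.** These cover not-related AEs (7.4.4.3, 7.4.4.8) and ADRs (7.4.4.5, 7.4.4.11). They include a row for "Gastrointestinal disorders" and placeholder rows for terms, but no vestibular row.
- **Event-level tables (7.4.4.6 to 7.4.4.8, 7.4.4.10, 7.4.4.11).** These use the total number of events as denominator and have no split by encounter.
- **Listings (7.4.4.9, 7.4.4.12).** These give patient ID, study timepoint and onset date for each event, ordered by organ class and preferred term.

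Protocol 2.1 sets out the tolerability background. It says that other broad-spectrum tetracyclines are often associated with "gastrointestinal, vestibular and phototoxic adverse effects and, in females, vaginal yeast infections" and that such events were generally uncommon with sarecycline.

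**The concern.** Safety and tolerability is a stated additional objective, and the background argument for the drug rests partly on a small set of class effects. A reader of SAP 6.8 expects a summary of how many subjects had GI or vestibular effects, and in which part of the 12 weeks. The shells would not print one.

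Three consequences follow:

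- The time pattern is collapsed into one column.
- The vestibular grouping is left open, so its terms could be chosen after the data are seen.
- The split by causality means that no summary gives the number of subjects with a given term whatever its cause.

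Separately, an event that only females can have is divided by everyone, so its printed rate is lower than the rate in those at risk.

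**Working it through.** The documents contain no calculated figure to reproduce. The 300 is a feasibility target used as a denominator; SAP 6.1 states that no power calculation was done. The check therefore compares text with shells and works through the denominators.

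**1. Encounter split.** SAP 6.8 and protocol 12.6.6 name Weeks 4, 8 and 12. No summary table has those columns. As an illustration, take first onsets at Weeks 4/8/12 of 12/2/1, 5/5/5 or 1/2/12. Each sums to 15, and each prints as 15/300 = 5.0%. Early and late patterns look the same.

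**2. Category.** GI is covered at organ-class level. For vestibular effects, neither document says which preferred terms belong to the group, and no shell has an aggregate row for them.

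**3. All-causality frequency.** Let a term be shown for *a* subjects in Table 7.4.4.3 and *b* subjects in Table 7.4.4.5. Each table counts a subject once per term, but the same subject may be in both. The number with the term in either table then lies between max(*a*, *b*) and *a* + *b*. With 6 in each (illustration), it lies between 6 and 12, or 6/300 = 2.0% to 12/300 = 4.0%. Table 7.4.4.1 combines both kinds of event but shows no terms.

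**4. Female-only events.** Let *f* be the female share, which is not in the documents and is assumed here. The printed rate is *k*/300 and the rate among females is *k*/(300*f*), so the understatement factor is 1/*f*. For *k* = 6 (illustration), the printed rate is 6/300 = 2.0% (exact 95% CI 0.7 to 4.3). With no events, the one-sided 95% upper bound is 1 − 0.05^(1/*n*), which is 0.99% for *n* = 300.

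| Assumed female share | Females | Rate for 6 events (exact 95% CI) | Factor 1/*f* | Upper bound, no events |
|---|---|---|---|---|
| 80% | 240 | 2.5% (0.9 to 5.4) | 1.25 | 1.24% |
| 60% | 180 | 3.3% (1.2 to 7.1) | 1.67 | 1.65% |
| 50% | 150 | 4.0% (1.5 to 8.5) | 2.0 | 1.98% |

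**5. Denominator for late intervals.** SAP 6.1 expects attrition but gives no rate. If 5% to 30% had left (assumption), 285 to 210 subjects would remain, and 6 subjects would be 2.1% to 2.9% rather than 2.0%. A fixed 300 would therefore be unsuitable once encounter columns are added.

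**The case against.** The strongest reply is that little is lost. Listings 7.4.4.9 and 7.4.4.12 carry timing and patient ID, so a reader could count by encounter and remove duplicates across the two causality groups. The X and Y rows are placeholders, so any coded term, vestibular or other, can have its own row with a subject-level percentage. A GI row exists. SAP 6.8 promises nothing specific on phototoxic or vaginal yeast effects. Tables 7.4.5 and 7.4.6 print the sex of adult and pediatric patients in the Safety Population, so a female rate can be worked out. The study is single-arm and descriptive.

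All of this stands. It rules out the stronger reading that the named class effects, or their timing, cannot be found at all. It does not supply the promised summary. A hand count from listings is not a tabulated frequency, and separate term rows are not a category aggregate.

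A reader might also infer that the fixed 300 hides patients who never took the drug. SAP 6.2 says of the Safety Population, "This in essence constitute all 300 Subjects recruited into the study", and protocol 6.4.1 allows for early loss: "In the event Subjects are unable to swallow the sarecycline tablets after enrollment, they will be discontinued from the study". The documents do not support that inference. The introduction to SAP section 7 and SAP 7.4 both describe the 300 as patients who took the drug, and Table 7.4.2 prints 300 (100%) for treatment on Day 1. The swallowing rule, and shipment of drug after the prescribing decision, show only that non-dosing was possible. If all 300 were dosed, 300 is a correct denominator for whole-study incidence in events that either sex can have.

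**Conclusion.** The text and the shells do not match. SAP 6.8 and protocol 12.6.6 commit to frequencies by category and encounter, and no summary shell provides them. The vestibular group is undefined, and the summaries cannot give the all-causality subject frequency of a term. These points rest on the documents alone.

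The female-only understatement follows from the denominator rule. Its size, 1.25 to 2 times, depends on an assumed female share of 80% to 50%. No general understatement of AE rates has been shown. This is a minor reporting improvement and does not threaten the safety conclusions.

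**What to change.** 1. Add Week 4, Week 8, Week 12 and overall columns to the subject-level AE and ADR tables. As the denominator for each interval, use the number dosed and still under observation at its start; Table 7.4.2 already plans closely related counts. State whether events are assigned by onset date or by reporting encounter, and where events after the Week 12 encounter go, since the table notes count events up to 30 days after the last dose.
2. List in advance the preferred terms that form the GI and vestibular categories, and the phototoxic category if it is reported. Use female patients as the denominator for female-only terms.
3. Add one subject-level organ-class and preferred-term table for all AEs whatever their causality, counting each subject once per term.
4. Optionally, replace the hard-coded 300 with the Safety Population count. Dosing should be confirmed from any source, such as the app date or a returned bottle. Relying on the app date alone could drop dosed patients who did not log it.

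The cost is table shells and programming. Event dates, coded terms, sex and disposition are already collected, and under protocol 7.3 to 7.5 investigators report AEs over the preceding four weeks at each follow-up encounter. Female-only rates will print higher.
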